For Task 2, graded mixed nerve injury recovery will also be evaluated. For partial transections, a 3-D printed nerve cutting guide will allow graded transections of 25%, 50%, and 75%. Controls of 0% and 100% mixed nerve crush or cut injury will be from Task 1. Again, we will use 12 rats per group, sacrificed on 4 separate dates, for a total of 48 rats per group (= 3 graded transections * 48 = 144 total additional rats).

For Task 3, two additional groups will be added: autograft and conduit repair. Again, we will include 12 rats per group, sacrificed on 4 separate dates, for a total of 48 rats per group (= 2 different repairs * 48 = 96 additional rats).

For all Tasks, a total of 576 rats will be required.

Aim 2: Determine if DTI fiber tracking can predict recovery of peripheral nerve function in human case studies (crush or cut with repair). Pure sensory, motor, and mixed nerves will be evaluated.

Using the studies from Aim 1 as model of failed nerve recovery, human *in vivo* MRI case studies will be performed. DTI data will be collected at 1, 3, 6, and 12 months after injury and surgical repair. The first time

point was chosen to allow for inflammation to subside, which can confound DTI-based estimates of nerve regeneration (edema can result in increased diffusivities that can be incorrectly interpreted as changes in myelination and/or axonal integrity⁶³). We expect that changes due to degeneration/regeneration will be detectable via DTI at this time, as previous case studies noted detectable differences as early as 1 month^{50,51} (as well as our preliminary data in Figs. 11,12). The final time point of 12 months was chosen to allow adequate time for nerve regeneration. This will yield a ground truth assessment of the success of the repair at the end of the study. DTI results will be correlated with results from nerve conduction and EMG studies if clinically indicated acquired at the 3-, 6- and 12-months after surgery. **We hypothesize that DTI will be able to stratify patients that are recovering versus patients with failed repair at earlier times points than nerve conduction and EMG.** An outline of the study is shown in Figure 13.

[figure not shown]

FIG 13. Study design timeline following surgical repair. MRI will be performed at 1, 3, 6, and 12 months after surgery to estimate DTI parameters. NCS/EMG data will be collected for comparison at 3, 6, and 12 months.

Patient Population

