Exclusion criteria: Patients will be excluded from enrollment if their injuries exhibit gross contamination, in circumstances where soft tissue coverage is inadequate, or when staged repair is planned. We will also exclude patients that are diabetic, have been diagnosed with a neuromuscular disease, or are undergoing chemotherapy, radiation therapy, or other treatments known to affect the growth of the neural and vascular system. We will exclude all patients currently enrolled in another investigational study or those who are unlikely to complete the normal regime of occupational therapy. For safety reasons, all pregnant women or women who are breast-feeding will also be excluded from this study along with subject with any ferromagnetic objects that cannot be removed (cardiac pacemakers, aneurysm clip, etc.), and/or a history of claustrophobia. All subjects will undergo a standardized MRI metal screening prior to each MRI scan, and signed consent will be obtained prior to all examinations.

Sample size: Previous optimization DTI studies in human median nerves reported mean (\pm SD) FA values of 0.7 ± 0.04 ⁴². We do not have human longitudinal data from which we can estimate an effect size; however, Takagi et al.²² performed ex vivo DTI in a rat injury model longitudinally and reported mean FA values of 0.5 following trauma (FA values are preserved across fixed and in vivo tissue⁶⁴). We, therefore, assume a similar mean FA value after surgery (0.5) with a SD taken from the aforementioned human optimization study (0.04) for our power analysis below. A conservative goal is to detect a 10% increase in FA from this decreased value to stratify successful from unsuccessful surgical interventions. If we test for

differences between these cohorts via a two-tailed pooled Student's t-test ($p = 0.05$), 24 patients would yield a study power of 0.8. Thus, assuming a failure rate of 40%, we will scan 24 patients, approximately 14 of which should have successful surgeries and 10 of which should have unsuccessful surgeries.

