Data Recorded	Study Entry	Postoperative Day				
		1	30	90	180	360
Demographics						
Age	X					
Sex	X					
Race	X					
Medical Comorbidities	X					
Surgical History	X					
Social History	X					
Worker's Compensation Status	X					
Occupation	X					
Concurrent Injuries	X					
Laboratory Values	X					
Rehabilitation Regimen		X	X	X	X	
Affected Limb Physical Examination	X	X	X	X	X	
Normal Limb Physical Examination	X		X	X	X	
Distance from Injury to Finger Tip	X					
Outcome Variables						
Pain Assessment	X	X	X	X	X	
Medical Research Council Classification	X	X	X	X	X	
Data Recorded	Study Entry					
Outcome Variables Continued						
Static 2-Point Discrimination	X	X	X	X	X	
Moving 2-Point Discrimination	X	X	X	X	X	
Michigan Hand Questionnaire	X	X	X	X	X	
Grip Strength	M	M	M	M	M	
Nine hole peg test		M	M	M	M	
Short Form 12	X	X	X	X	X	
Dash Questionnaire	X	X	X	X	X	
Complications		X	X	X	X	
MRI			X	X	X	

X = ALL COHORTS, M= MIXED NERVE

DTI Analysis

In each subject, we will acquire 15 diffusion-weighted (DW) volumes, each sensitized to diffusion along a different direction, along with a non-DW volume as described above. All DTI pre-processing and tensor estimations will be performed via FMRIB's Software Library (FSL)⁶⁹. All volumes will first be coregistered to the non-DW volume using a 3D affine transformation to correct for the effects of motion and eddy currents. If rotations to the data are applied, the gradient table will be rotated accordingly. Then, the diffusion tensor **D** will be calculated using a weighted linear least squares approach. Three eigenvalues and corresponding eigenvectors will be calculated from **D**, defining the diffusivities and principal direction of diffusion, respectively. From this, we will calculate the FA, MD, RD, and AD on a voxel-wise basis. As a reminder, MD represents the mean diffusivity across all directions, AD represents diffusivity parallel to the principal directions of the axons, RD represents diffusivity parallel to the principal directions of the axons, and FA quantifies the degree of diffusion anisotropy. During regeneration, we expect to observe an increase in FA and decrease in MD due an increase in the order and total number of diffusion barriers, respectively. The relative impact of RD and AD on these changes has yet to be established; however, it has been suggested that RD primarily reflects myelination, while AD primarily reflects axonal degeneration/regeneration^{22, 53}.

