The eigenvalues/eigenvectors estimated from **D** will also be used to perform fiber tractography, which will be performed using the ExploreDTI toolbox⁷⁰. Seed regions-of-interest (ROIs) of each nerve will be drawn

in the most proximal slice to seed each fiber tract. FA threshold values and the angulation tolerances determine the limits for the automatic tracking of fibers. Previous work⁴³ has determined optimal reconstruction parameters for fiber tractography of healthy nerves (FA threshold = 0.2 and maximum angulation tolerance = 10). We will use these parameters as a starting point, noting that adjustments may need to be made in regenerating nerve. Tractography results will be quantified by estimating the mean length of fiber tracts as well as the relative number of fiber tracts that successfully reach ROIs defined in the most distal slice. During regeneration, we expect mean fiber lengths and relative tract numbers to increase.

Statistics

Statistical analyses will be performed using STATA/IC 13.1 (StataCorp, College Station, TX). In controls, tests will be performed to evaluate i) the relationship between DTI metrics and confounding variables (age, sex, and BMI), ii) the variability of DTI metrics between nerves and along nerve segments and iii) the repeatability of DTI metrics across scans and raters. In patients, tests will be performed to i) evaluate the ability of DTI to predict failed nerve recoveries at each time point (using evaluations at 12 months as the ground truth) and ii) evaluate correlations between the DTI parameters and EMG/NCS results.

We will first examine the potential confounding influence of BMI, age, and sex on each DTI parameter via multiple linear regression in controls. A Shapiro-Wilk test on the regression residuals will be used to test for normality. For the sake of this proposal, we assume normality and that parametric statistical tests are appropriate. We will employ corresponding non-parametric tests if normality is not observed. The effects of BMI, age, and sex on DTI parameters will be quantified via Pearson partial correlation coefficients. To test for variations across nerve and along nerve segments in control subjects, an ANOVA will be performed. If significant variation is observed, post hoc pair-wise comparisons will be performed using a Bonferroni multiple comparison test.

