To understand the ability of DTI parameters to provide estimates of nerve regeneration, it is important to first understand the reliability of the acquisition (interscan) and assessment (interrater) methodology. To estimate the interscan reliability, intraclass correlation coefficients (ICC) will be calculated for each DTI metric in the control scan-rescan data. To test for changes in DTI parameters across time, paired t-tests will also be performed between each timepoint. Finally, the interscan variabilities of DTI parameters will be estimated via the repeatability coefficient (RC), which is defined as 1.96 times the SD of the mean difference between scans. Analogous analyses will be performed for the inter-rater data, where nerve ROIs will be independently defined in 12 control subjects by two trained raters.

Patients will be grouped into “failed” or “successful” cohorts based upon our evaluations at 12 months. All tests below will be performed in three nerve segments of the injured nerve: i) proximal to the injury, ii) at the injury site, and iii) distal to the injury. The percent difference in DTI parameters between injured and non-injured arms will be used in all analyses to control for confounding factors (e.g., age). To evaluate the ability of DTI to predict failed nerve recoveries at each time point, we will perform two sets of test. First, significant difference between “failed” or “successful” groups will be tested (at each time point and nerve segment) via a Bonferroni multiple comparison test. Second, and ROC analysis will be performed to evaluate the diagnostic potential of each normalized DTI parameter at each time point and nerve segment. Finally, to evaluate relationships between DTI parameters and NCS/EMG data (e.g., CMAP), pairwise Pearson correlations and Bonferroni corrected significance values will be calculated.

Potential Pitfalls/Solutions

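### The power of 0.8 belongs to one uncorrected t-test on raw FA; the planned analysis is a Bonferroni-corrected percent difference over visits and segments, with no primary comparison or family size stated.

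*Combined protocol and SAP*

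**What the plan says.** The Sample size paragraph (Aim 2, Patient Population) assumes a mean FA of 0.5 after surgery, "with a SD taken from the aforementioned human optimization study (0.04"), and a 10% rise as the difference separating successful from failed repairs. With a two-tailed pooled t-test at 0.05 and a 40% failure rate (about 14 successes and 10 failures), it states that "24 patients would yield a study power of 0.8". No visit or nerve segment is attached to this test.

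The Statistics section describes the patient analysis differently:

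- **Variable:** "The percent difference in DTI parameters between injured and non-injured arms will be used in all analyses to control for confounding factors".
- **Segments:** "All tests below will be performed in three nerve segments of the injured nerve" (proximal, injury site, distal).
- **Test:** the failed and successful "groups will be tested (at each time point and nerve segment) via a Bonferroni multiple comparison test".

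Aim 2 sets the visits: "DTI data will be collected at 1, 3, 6, and 12 months after injury and surgical repair". The DTI Analysis section adds further metrics: "we will calculate the FA, MD, RD, and AD on a voxel-wise basis". Nothing in the document names a primary metric, visit or segment, says how many tests the Bonferroni correction covers, or gives an SD for the percent difference.

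**The concern.** The 0.8 sets N at 24 and is the only power figure for the human study, but it describes a test that the Statistics section does not plan. Three features differ: the variable (raw FA versus a between-arm percent difference), the number of tests (one versus 12 per metric) and the significance level (0.05 versus a corrected level of unstated size).

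The Bonferroni sentence can also be read in two ways. It may spread alpha over segments, visits or both. Or it may apply inside each cell, as in the control analysis of the same section, where "post hoc pair-wise comparisons will be performed using a Bonferroni multiple comparison test" after an ANOVA. With two outcome groups there is only one pair per cell, so on that reading nothing is corrected across the 12 cells.

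At stake are the chance of detecting the planned difference, the false-positive rate, and the interpretation of the main hypothesis that DTI separates recovering from failed repairs earlier than NCS/EMG. With no named primary, the plan does not say which of the results decides that hypothesis.

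**Working it through.** **Inputs from the plan.** FA 0.50 versus 0.55 (10% of 0.50), SD 0.04, 14 versus 10 patients, two-sided 0.05, 4 visits, 3 segments, 4 tensor metrics (FA, MD, RD, AD).

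**1. The stated figure.** Standardised difference d = 0.05/0.04 = 1.25; df = 14 + 10 − 2 = 22; noncentrality = 1.25 × √(14 × 10/24) = 3.02. Noncentral-t power at two-sided 0.05 is **0.82**. At a 60:40 split, 23 patients give 0.797, so 24 is the smallest N that reaches 0.80. The plan's arithmetic is right for that test, with almost no slack.

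**2. Bonferroni across cells, same raw-FA inputs.** Only alpha changes, to 0.05/m.

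| Family | m | Power per comparison | Difference detectable at power 0.80 |
|---|---|---|---|
| One test | 1 | 0.82 | 9.7% |
| Segments | 3 | 0.67 | 11.5% |
| Visits | 4 | 0.62 | 11.9% |
| Visits × segments, FA only | 12 | 0.45 | 13.6% |
| Visits × segments × 4 metrics | 48 | 0.27 | 15.6% |

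The last column is the d that gives power 0.80, times 0.04/0.50; for m = 12 this is 1.695 × 0.08 = 13.6%, against the plan's goal of 10%.

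**3. Bonferroni within each cell.** Each of the 12 cells is tested at 0.05 and power stays at 0.82. If no cell has a true difference and the cells are independent, the chance of at least one false positive is 1 − 0.95¹² = 0.46. Simulation (100,000 runs) with an assumed common between-cell correlation of 0.5 or 0.8 gives 0.33 or 0.19.

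**4. The percent-difference scale.** The plan gives no SD here, so this step rests on assumptions: an uninjured-arm FA of 0.70 with SD 0.04 (the healthy-nerve figure quoted in the Sample size paragraph), SD 0.04 in the injured arm, and a between-arm correlation ρ. The effect is 100 × 0.05/0.70 = 7.14 points. By the delta method, the SD in a group with injured-arm mean μ is (100 × 0.04/0.70) × √(1 + r² − 2ρr), where r = μ/0.70. The two group SDs are then pooled with weights 13 and 9.

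| ρ | Pooled SD (points) | Power, m = 1 | m = 3 | m = 12 |
|---|---|---|---|---|
| 0 | 7.17 | 0.63 | 0.44 | 0.25 |
| 0.3 | 6.05 | 0.78 | 0.61 | 0.39 |
| 0.5 | 5.17 | 0.89 | 0.77 | 0.57 |
| 0.7 | 4.10 | 0.98 | 0.94 | 0.83 |
| 0.8 | 3.44 | 1.00 | 0.99 | 0.95 |

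Power of 0.80 requires an SD of at most 7.14/1.214 = 5.9 points (m = 1), 7.14/1.434 = 5.0 (m = 3) or 7.14/1.695 = 4.2 (m = 12). These correspond to ρ of about 0.34, 0.54 and 0.68.

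**5. Limits of step 2.** Those are powers for a single named cell. If the 10% difference is present in several cells, the chance of at least one true positive at 0.05/12 is higher: 0.61 to 0.83 for one segment at three visits, and 0.70 to 0.97 for two segments at three visits (between-cell correlation from 0.8 down to 0). Larger differences also help: at 0.05/12, power is 0.89 for a 15% difference and 0.995 for 20%.

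**The case against.** The strongest reply is that the stated 0.8 is not wrong. It reproduces, its inputs are presented as assumptions, and the plan admits that it has no human longitudinal data. Aim 2 is framed as case studies, where the lack of one primary comparison matters less than in a confirmatory trial. This limits the seriousness but does not remove the gap: the plan still states a directed hypothesis, a correction and a power.

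Second, Bonferroni on a single two-group test does nothing, so correction across cells is the more natural reading, and the false-positive figures in step 3 should carry less weight. That is fair. But the across-cell reading is the one that lowers power per comparison.

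Third, 12 is not the only possible family. The 12-month scan coincides with the assessment that defines success, so it cannot show earlier prediction. Dropping it leaves 9 tests and power 0.49. N might also exceed 24 if the additional pure-motor cases (unlikely to exceed 10) are pooled, which the plan does not say. With 20 versus 14 patients, power is 0.82 for 4 tests and 0.69 for 12. So pooling would restore 0.8 for a small family but not for 12 tests.

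Fourth, normalising to the uninjured arm is a design strength. Above a between-arm correlation of about 0.38 it raises power relative to raw FA. This stands, and it is why the 0.8 cannot be called too high on that scale.

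Finally, Aim 2 refers to fibre tracking, so FA is not the only candidate primary, and the ROC analyses by metric, visit and segment carry no stated correction either. Both points are sound. FA is used here because it is the metric the plan powered.

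**Conclusion.** The concern holds. The stated power is correct for a test that the plan does not propose to run, and the planned test is not shown to have it. On the plan's raw-FA inputs, a Bonferroni correction over 3 to 12 tests lowers power per comparison from 0.82 to between 0.67 and 0.45; pooling four metrics gives 0.27. Without correction across cells, power is kept but the error rate over 12 cells is roughly 0.19 to 0.46. On the percent-difference scale, power ranges from 0.63 to 1.00 uncorrected and from 0.25 to 0.95 for 12 tests, for between-arm correlations of 0 to 0.8.

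The raw-FA powers follow from the plan's figures once a family size is chosen. The between-cell correlation, the between-arm correlation and the use of 0.70 (SD 0.04) for the uninjured arm are assumptions. This should be fixed before analysis; it does not show that 24 patients are too few.

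**What to change.** 1. Before analysis, name one primary FA comparison (one visit, one segment) on the percent-difference scale at two-sided 0.05. The sponsor should choose the visit in light of the hypothesis of earlier detection than NCS/EMG and the caution about early inflammation in Potential Pitfalls/Solutions. The NCS/EMG schedules should be reconciled first: Aim 2 and the Figure 13 legend start at 3 months, while Investigational Procedure includes 1 month.
2. Make all other visits, segments and metrics secondary, and state which tests form the Bonferroni family and how many there are.
3. Restate power for the percent difference over a stated range of SD and between-arm correlation.
4. If no primary is named, replace the single 0.8 with a range of power at the corrected alpha on the percent-difference scale, and state the family size.

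The cost is SAP wording only, with no added patients or scans. Naming a primary moves the other results to secondary status; not naming one means reporting a range that may be less favourable than 0.8.

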Subject recruitment: Patients will be recruited through consultations to the hand service at VUMC. Patients scheduled to receive nerve repair procedures meeting the criteria will be considered for participation. All patients must give informed consent prior to any study procedures. In the case of patients who are not competent to make a decision regarding study participation, they will be excluded from the study. A copy of the signed study consent document and authorization forms will be given to each patient. All signed consent documents will be stored in a locked cabinet in the office of the research coordinator or Principal Investigator, [name]. In an average year, the Vanderbilt Medical Group performed over 372 digital nerve repairs and an additional 50 repairs involving mixed nerve loss in the upper extremity. As a result, we anticipate reaching our target recruitment of 24 mixed injury subjects within approximately 18 months, leaving adequate time for sequence development in the early stages of the award (1st six months) and 12-month follow-up scan in the latter stages of the award (3rd year). It is rare to see a pure motor nerve injury (ulnar motor branch of the hand). These ulnar motor branch injuries will be additionally included through the duration of the study, but it is unlikely that more than 10 will be observed in a single center study.

Investigational Procedure

After inclusion criteria are met, a standard peri-operative anesthesia evaluation will be undertaken. If the patient is deemed to be of appropriate operative risk to undergo immediate operative repair, informed consent will be obtained and patients will be enrolled in the study. These determinations and obtainment of informed consent will be by research coordinator or principal investigator. It is anticipated that patients will be enrolled primarily through the emergency and trauma units. Clinical testing will occur as scheduled in Table 1. EMG/NCS will be performed after injury if clinically indicated, and at 1,3,6, and possibly 12 months after injury. These studies will be limited to focus on the injured nerve to decrease exam time and discomfort. If patients have fully recovered clinically, additional EMG's will not be performed.

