As previously mentioned, we expect to be able to meet our subject recruitment targets (24 subjects) within the first two years of the award, allowing one additional year for follow-ups. If we encounter recruitment (or retention) issues, we will investigate the feasibility of performing DTI in the digital nerves of the hand, as injury to these nerves is much more common. Our preliminary studies indicate that our DTI protocols have sufficient resolution to robustly perform DTI of the nerves at the level of the wrist. Performing tractography from these larger, more proximal nerves (median and ulnar) to the more distal digital nerves of the hand may also be feasible, and will be investigated if recruitment and/or retention issues are encountered.

In interpreting our DTI results in patients, it is important to consider each DTI metric’s specificity to different pathological processes. Although diffusion metrics are primarily sensitive to axonal integrity, studies

have shown the DTI indices are also sensitive to myelination and inflammation^{63, 65}. Given that all of the processes may occur concurrently during nerve degeneration/regeneration, a direct linkage between changes in DTI parameters and nerve recovery may be difficult, especially at the earlier time points when some level of inflammation may be present. Although histological evaluation of these various processes is not feasible in humans, we have a number of validated quantitative measures (EMG, NCS) that, when available, can be used to validate our DTI findings in humans. In addition, we will rely on the proposed validation studies in animal models (Aim I) to better understand the relationship between our DTI observations and underlying pathology.

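### EMG testing stops at full clinical recovery, so late DTI–EMG/NCS correlations leave out fully recovered patients and probably understate a linear relationship

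*Combined protocol and SAP*

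**What the plan says.** All references are to the combined protocol and SAP.

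- **Investigational Procedure** sets the schedule, "EMG/NCS will be performed after injury if clinically indicated, and at 1,3,6, and possibly 12 months after injury", and then the stopping rule: "If patients have fully recovered clinically, additional EMG's will not be performed". It gives no threshold for full clinical recovery. The rule names EMG; whether NCS also stops is unclear.
- **Aim 2** describes a different schedule: "DTI results will be correlated with results from nerve conduction and EMG studies if clinically indicated acquired at the 3-, 6- and 12-months after surgery". The **Figure 13 caption** has a third, with no condition: "NCS/EMG data will be collected for comparison at 3, 6, and 12 months". Both place MRI at 1, 3, 6 and 12 months, with no stopping rule.
- **Statistics**, on DTI against NCS/EMG: "pairwise Pearson correlations and Bonferroni corrected significance values will be calculated". It does not say whether these are computed per visit or pooled, and has no rule for EMG/NCS missing because of recovery.
- **Potential Pitfalls/Solutions** accepts that EMG/NCS will sometimes be absent, since these measures "when available, can be used to validate our DTI findings in humans". It does not address why they would be absent.

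**The concern.** A pairwise correlation uses only patients with both values. Once a patient has fully recovered, DTI is still collected but the electrodiagnostic partner is not, so the pair disappears. The lost pairs are not a random subset. They come from the patients judged best recovered, and cutting off one end of a range generally shrinks a Pearson coefficient when the relationship is linear. The number of pairs falls as well.

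Histology is not feasible in the human part, and the plan names EMG and NCS as validated measures against which to check DTI. A weak coefficient at month 6 or 12 could be read as DTI failing to track recovery when the testing rule had produced it. The same gap touches the Aim 2 hypothesis, which sets DTI against both electrodiagnostic tests: "We hypothesize that DTI will be able to stratify patients that are recovering versus patients with failed repair at earlier times points than nerve conduction". Fully recovered patients have no later EMG for that comparison.

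**Working it through.** **1. The plan's own figure.** The Sample size paragraph gives 24 patients (about 14 successes, 10 failures), FA difference 0.05 (10% of 0.5), SD 0.04, two-sided 0.05, power 0.8. The noncentrality is 0.05 / (0.04 × √(1/10 + 1/14)) = 0.05 / 0.01656 = 3.02 on 22 degrees of freedom, so power is 0.82. The smallest total reaching 0.80 is 23 (10 and 13, power 0.81). The figure reproduces and this point does not affect it. The plan states no power or expected r for the DTI–EMG/NCS correlation, so what follows rests on assumptions.

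**2. Attenuation formula.** Let E be EMG/NCS, D a DTI parameter and C clinical recovery, jointly normal. Remove the top share p on C. With c the normal quantile at 1 − p, h = φ(c)/(1 − p) and g = c·h + h²:

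r among those still tested = (ρ_ED − ρ_EC·ρ_DC·g) / √[(1 − ρ_EC²·g)(1 − ρ_DC²·g)]

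Assume ρ_ED = 0.6 and 7 of 24 stopped. Then p = 0.292, c = 0.549, h = 0.485 and g = 0.266 + 0.235 = 0.501.

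- Clinical recovery orders patients exactly as EMG/NCS (ρ_EC = 1, ρ_DC = 0.6): (0.6 − 0.301) / √(0.499 × 0.820) = 0.47.
- ρ_EC = 0.7, DTI linked to clinical recovery only through EMG/NCS (ρ_DC = 0.7 × 0.6 = 0.42): (0.6 − 0.147) / √(0.755 × 0.912) = 0.55.
- ρ_EC = 0.7, DTI also tracking clinical recovery directly (ρ_DC = 0.6): (0.6 − 0.210) / √(0.755 × 0.820) = 0.50.

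These are large-sample values. With 17 pairs left, the average sample coefficient is slightly lower: about 0.46 in the first case and 0.48 to 0.53 across the other two. With nobody stopped it is 0.59.

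**3. Size under exact ordering** (simulation, n = 24, true r = 0.6, test at uncorrected 0.05):

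| Stopped | Pairs | Critical r | Mean r | Power |
|---|---|---|---|---|
| 0 | 24 | 0.404 | 0.59 | 0.90 |
| 7 | 17 | 0.482 | 0.46 | 0.51 |
| 14 | 10 | 0.632 | 0.37 | 0.21 |

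The last row requires every expected success to be fully recovered and untested, so it is an upper bound. If clinical recovery correlates 0.8 with EMG/NCS and 7 stop, mean r is 0.52 and power 0.63. Bonferroni correction would lower power further.

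**4. Direction.** Under a linear relation (assumed r = 0.7, 20% or 40% removed), the reduced-sample r falls below the full-sample r in about 73 to 85% of single samples of 24, so not always. Two departures reverse the expected direction:

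- DTI flat over the top 40% of recovery: r is 0.58 in all patients and 0.63 in those still tested.
- EMG still abnormal in clinically recovered patients whose DTI is normal (20% recovered): 0.51 in all and 0.70 in those still tested.

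**5. Testing a remedy.** Keep all 24 patients in a rank correlation and give those stopped for recovery a shared best EMG/NCS rank (true r = 0.6).

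- Exact ordering: mean 0.55 (7 stopped) or 0.50 (14 stopped), power 0.83 or 0.74, better than complete pairs.
- ρ_EC = 0.7, DTI linked only through EMG/NCS, 14 stopped: 0.39, against about 0.50 for complete-pairs Pearson.
- No true DTI–EMG correlation, but each correlated 0.5 with clinical recovery: mean 0.23 (7) or 0.33 (14), with false-positive rates of 19% or 37%. Complete-pairs Pearson is itself biased there, to about −0.13 to −0.20, with a false-positive rate near 8.5%.

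Neither analysis is safe alone; reported together, they show how far the answer depends on the missing values.

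**The case against.** The stopping rule catches only the fully recovered. Partly recovered patients who count as successes stay in, and if visits were pooled, earlier EMG/NCS from patients who recover later would still contribute. A reader might infer that the late correlations contain only patients who have not recovered, or that they will certainly understate the relationship. The documents support neither: the first overstates the rule, and the second depends on the shape of the relationship (step 4).

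A reader might also infer that EMG/NCS is the only quantitative check on DTI in humans. It is not. The Statistics section tests DTI against 12-month success or failure by group comparison and ROC analysis, and Table 1 lists two-point discrimination, grip strength and a peg test. The correlation is also not the comparison on which the sample size rests. Nor do the documents say that EMG/NCS feeds the 12-month classification, so no claim can be built on that.

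The ambiguity over NCS matters too, because the plan's example measure, CMAP, comes from NCS. If NCS continued, that part of the correlation would be unaffected. Timing could limit the loss: the Significance section says recovery may take up to a year, though its example is a grafted elbow-level injury and eligible injuries here lie at mid-forearm or beyond.

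These arguments limit the size and certainty of the effect. They do not remove it: testing stops on outcome, MRI does not, and the analysis has no rule for the resulting gap.

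**Conclusion.** The point holds as a probable bias of unknown size in a supporting analysis. If the plan is followed as written, any visit-specific DTI–EMG/NCS correlation after stopping omits the fully recovered patients and does not represent the cohort. Understatement is the likelier direction if the relationship is linear. For an assumed true r of 0.6 with 7 of 24 stopped, expect about 0.46 under exact ordering and about 0.48 to 0.53 if clinical recovery and EMG/NCS correlate 0.7. The number stopped, the true r and the link between clinical recovery and EMG/NCS are all assumptions. If NCS continues after recovery, only the EMG part is affected. The failed-versus-successful comparison and its power are untouched. The gap should still be closed before analysis, because a weak late coefficient is easily misread.

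**What to change.** Leave the testing rule as it is and change the analysis text in Statistics:

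1. State that DTI–EMG/NCS correlations are computed per visit.
2. Record the reason for each missing EMG or NCS, with full clinical recovery as a separate category.
3. Keep the complete-pairs correlation, but label it at months 6 and 12 as applying to patients not fully recovered, and report the number recovered and untested.
4. Beside it, prespecify a sensitivity rank correlation over all patients in which those stopped for full recovery share the best rank. State that it assumes clinical recovery tracks EMG/NCS and can overstate or understate r if it does not.
5. State that a low late complete-pairs coefficient will not be read as DTI failing to track recovery unless the two analyses agree.

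Moving the main correlation to month 3 is not a good substitute. The background sections describe EMG/NCS as of limited use until target reinnervation and describe absent responses after transection, so many values may be at their floor then.

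The sponsor should also reconcile the EMG/NCS schedule across Aim 2, the Figure 13 caption and Investigational Procedure, say what full clinical recovery means for this rule, and say whether the rule covers NCS.

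The cost is one extra analysis, one data field and a few sentences, with no additional tests for patients.
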